Cover Page

Study Title: Effects of fermented vegetables on gut microflora and inflammation in women

NCT03407794

Date: July 5th, 2019

Cover Page

Study Title: Effects of fermented vegetables on gut microflora and inflammation in women

NCT03407794

Date: July 5th, 2019

Effects of fermented vegetables on markers of inflammation and composition of the intestinal microflora in overweight and obese women

Principal investigator: [name], MPH, RDN – Department of Nutrition & Dietetics

Abstract

Overweight and obese individuals seem to have an altered profile of the gut microflora compared to normal weight individuals. This proposal will examine whether daily consumption of fermented vegetables for 6 weeks can impact the gut microflora and markers of inflammation of overweight and obese women.

Problem to be studied and its significance

Despite significant research efforts from the public and private sectors to reduce the burden of obesity, it continues to affect individuals worldwide [1]. In the United States, the prevalence of obesity among U.S. adults during 2011-2014 was 36.5% [2]. It is worthy to note, however, that during this period, the prevalence of obesity in women aged 20 to 59 years was significantly higher than in men (38.3% in women versus 34.3% in men), and if race is taken into consideration, non-Hispanic black women have the highest prevalence of obesity (56.9%) followed by Hispanic (45.7%), and non-Hispanic white women (35.5%) [2].

Over the last decade there has been an increasing interest in the relationship between the intestinal microflora and obesity as several research studies have shown an association between obesity and changes in the composition of the intestinal microflora [3-6]. For example, *Bifidobacteria*, which are regarded as probiotic bacteria that confer health benefits to the host, are found to be decreased in fecal samples of overweight and obese subjects compared to lean subjects [7]. In addition, obese subjects seem to have a

lower ratio of *Firmicutes* to *Bacteroidetes*, which are some of the most abundant bacterial phyla present in the human gut [8]. Some studies suggest that the altered intestinal microflora profile of obese individuals may lead to an increase in production of lipopolysaccharide (LPS) endotoxin, which is derived from the cell wall of gram-negative bacteria in the gut (such as the *Bacteroidetes* mentioned earlier) and induces an inflammatory response by the body [9]. This may be one reason why overweight and obese individuals often present elevated levels of inflammatory markers in the blood, including LPS [10] and other more established markers of inflammation such as C-reactive protein (CRP) [11].

The composition of the intestinal bacteria is influenced by several factors, including host genotype, age, sex, antibiotic/medication use, disease, and diet. Changes in the intake of specific food components may lead not only to changes in the gut bacteria but may also lead to changes in gene expression of different tissues in the host, which may be directly related to more or less fat storage [12]. For example, a cross-over study looking at the effects of consumption of 4 weeks of fermented kimchi and 4 weeks of fresh kimchi in obese Korean subjects (7 male and 15 female) found significant decreases in body weight, and body fat after consumption of fermented and fresh kimchi. In addition, decreases in blood pressure, percent body fat, fasting glucose, and total cholesterol were significantly greater during the fermented kimchi phase compared with the fresh kimchi phase [13]. In a parallel arm study conducted with overweight and obese Korean women, consumption of both fermented and fresh kimchi resulted in a decrease in the *Firmicutes* to *Bacteroidetes* ratio and in the relative abundance of *Bifidobacteria*, even though there were no significant differences between groups in body weight or inflammatory markers [14]. The findings from these Korean studies suggest that fresh and fermented kimchi may have different effects on intestinal bacteria and metabolism of the host. Unfortunately, very few studies examining the effects of fermented foods on metabolic parameters have been conducted in the U.S., likely due to the low consumption of fermented vegetables by the population. The present study was designed to investigate

the effects of fermented vegetables on the composition of the gut microflora and other biological and clinical parameters associated with obesity and other chronic diseases.

Study Aims

Aim 1: To examine the effect of daily consumption of fermented vegetables compared with non-fermented vegetables for 6 weeks on markers of metabolic syndrome and inflammation of overweight and obese women.

Hypothesis 1: Consumption of fermented vegetables will improve markers of metabolic syndrome (blood pressure, insulin, adiposity) and inflammation, such as C-reactive protein (CRP), and lipopolysaccharide (LPS) in overweight and obese women.

Aim 2: To examine the effect of daily consumption of fermented vegetables compared with non-fermented vegetables for 6 weeks on the profile of the gut microflora.

Hypothesis 2: Consumption of fermented vegetables will lead to a shift in microbial communities towards an increase in communities regarded as probiotics such as Bifidobacteria and Lactobacilli.

Significance

Obesity continues to be a major public health burden and its consequences have a significant impact on disease risk and quality of life, particularly in women who are more affected by this problem than men. Several weight loss interventions have been tested in the past 30 years, but it does not seem that a great impact in obesity treatment has been made so far. This is partially due to the fact that weight loss trials have a transient positive effect, which gets reversed as soon as the intervention stops. Due to these challenges faced by traditional weight loss trials, there is a need to look for alternative approaches to reduce the burden of obesity, particularly in women. Although it is now well recognized that there is a

strong relationship between the gut bacteria and obesity, there is a lack of feeding studies aimed at altering the composition of the gut bacteria via consumption of fermented foods. In addition, most of the studies examining the effects of fermented foods on health and disease parameters have been conducted in Asian countries, where the consumption of fermented foods like kimchi and soy products is high compared with Western countries. This proposal addresses the gap in the research with fermented foods that exists in the U.S. by examining the effects of consumption of fermented vegetables on several markers associated with obesity in women.

Methodology and analysis

Methodology

Study design: This will be a parallel arm study where 39 women will be randomized into one of three treatment groups: a fermented vegetable group (n=13), a non-fermented vegetable group (n=13), and a control group (n=13). The duration of the study will be 6 weeks and women in the vegetables groups will be asked to consume 1 cup of vegetables (140 g) per day for the entire duration of the study as well as follow their usual diet. Women randomized into the control group will be asked to follow their usual diet. Biological samples including feces and blood samples will be collected at baseline, before randomization and at the end of the 6-week intervention.

Study participants: Thirty-nine overweight and obese women aged 20-59 years will be recruited for this study. The table below shows inclusion and exclusion criteria for the study:

INCLUSION CRITERIA	EXCLUSION CRITERIA
BMI: 26-40 kg/m ²	BMI < 26 kg/m ²
Non-smoker	Smoker

No previous diagnosis of cancer	Taking medications that affect appetite or body weight
No thyroid disease	Uncontrolled Hypertension
No diabetes	Diabetes
Willing to consume 1 cup of vegetables daily for 6 weeks	Not willing to consume 1 cup of vegetables daily for 6 weeks
No use of psychotic or depression medication	Willing to show up at two appointments
No medication to lose weight	Following a fad diet
Not on a weight loss diet	Using antibiotics frequently
No use of antibiotics over the past 3 months	Diagnosed with autoimmune disease, like psoriasis, rheumatoid arthritis, thyroid disease, colitis
No consumption of fermented vegetables on a regular basis	Regular consumption of fermented vegetables
No history of autoimmune disease, including gastrointestinal disease	

Study procedures: Participants will be recruited by posting flyers at UNF Women's Center and in Jacksonville Women's clinics, as well as by newspaper advertisements. Interested participants will be asked to contact the study via email sent to an email account that will be created for the study. Upon receiving emails from interested participants, study staff will conduct a screening interview to ensure eligibility for the study. If women are found to be eligible after the initial screening interview, a screening clinic visit for verification of eligibility status will be scheduled. At the screening clinic visit all the study

procedures will be explained in detail, and participants will be asked to sign the consent form if they agree to participate. Blood and stool samples will be collected and once all eligibility criteria are confirmed, participants will be randomized into one of the three groups and arrangements will be made for weekly pick up/delivery of vegetables to those in the vegetables groups.

Vegetables preparation: Fermented vegetables for the entire study will be provided by a local producer weekly, whereas non-fermented vegetables samples will be obtained at a local grocery store. The process of vegetable fermentation involves *Lactobacilli* and *Bifidobacteria* that are naturally found on the leaves of cabbage, carrots and on cucumbers. These bacteria are able to convert the carbohydrates present in these vegetables into lactic acid under anaerobic conditions. The lactic acid is responsible for the acidic flavor of the fermented vegetables. The non-fermented vegetables will serve as a positive control for the fermented vegetable group, because it will have a similar flavor but no live microorganisms, mainly because store-bought pickled vegetables and sauerkraut are made by a different process that uses acetic acid, instead of live bacteria. Vegetable samples will be portioned by study staff using food safety precautions and delivered to participants weekly.

Biological sample collection: Blood samples will be collected in red top tubes to obtain serum for determination of insulin, CRP, and LPS. CRP will be measured using a commercial ELISA kit (Cat#DCRP00, R&D Systems, Minneapolis, MN). LPS will be measured using Pierce LAL chromogenic endotoxin quantitation kit (Cat#88282, ThermoFisher Scientific, Waltham, MA). All analyses will be conducted in [name] laboratory, which is already set up for these measurements. Stool samples will be collected to analyze the composition of the gut bacteria. Participants will receive a stool collection kit prior to the initial screening visit and they will be asked to bring the stool sample to the screening visit.

Survey data collection: Participants will be asked to fill out several surveys to assess food intake, demographics, and prescription medication intake. The diet history questionnaire, which is a 120-item food frequency questionnaire designed by the National Cancer Institute [15] will be used to assess baseline and follow-up dietary intake of participants. Participants will also receive daily logs to monitor gastrointestinal function (frequency of defecation and consistency of stools) and possible side effects of consumption of fermented vegetables such as bloating, diarrhea, constipation, and headache.

Clinical data collection: Height will be measured in centimeters using a Detecto 439 Eye Level Beam Physician Scale 400lb x 4oz with Height Rod. Weight and %body fat will be obtained via Bioimpedance (Tanita BC-532). Sagittal abdominal diameter (a measure of visceral obesity) will be assessed using a Holtain-Kahn caliper. Blood pressure will be measured using a Digital blood pressure monitor (Omron HEM907XL).

Compliance: To assess compliance in the vegetables groups, participants will be asked to fill out logs where they will check whether they consumed the vegetables for the day or not. Participants will also be asked not to discard any vegetables that have not been consumed. These containers will be picked up weekly at the time participants receive their following week's supply. This will allow us to quantify the amount of vegetables that is truly consumed by the participants every week.

Microflora analysis: Stool samples will be stored at -70C until DNA extraction. DNA will be extracted using the QIAamp DNA stool mini kit (Qiagen, Hilden, Germany) and samples will be stored until analysis of microflora. Analysis of microflora in stool samples and vegetables samples will be conducted

in the laboratory of [name] at St. Cloud State University. This type of analysis is currently not being performed at UNF, therefore, [name] will be working on a contract to have the samples measured at St. Cloud State University. Drs. [name] and [name] have had a working relationship since 2012 when they worked on a study related to fermented wheat bran and its effects on the composition of the gut microflora at the University of Minnesota.

Analysis

Treatment groups will be compared at both times points using analysis of variance. Changes from baseline within treatment groups in clinical and laboratory measures will be compared by paired *t* tests. Pearson's correlation coefficients will also be calculated between clinical and laboratory parameters and alterations in the intestinal microflora.

Plan for dissemination of results

The findings from this project will be disseminated in three different ways: via open access peer-reviewed manuscripts, poster presentations at scientific meetings, and via UNF newspaper. It is also expected that this project will originate pilot data to apply for external funding from institutions such as the Obesity Society and the American Heart Association.

Timeline

Project activities	Year 1				Year 2			
	Q1	Q2	Q3	Q4	Q1	Q2	Q3	Q4
IRB application and approval								
Recruitment and enrollment of participants								
Intervention/data collection								

Sample preparation for analysis and shipping							
Intestinal microflora analysis at St. Could State University							
Statistical analysis							
Manuscript preparation and dissemination							

Project budget (\$14,975.65)

Undergraduate research assistant (\$1,431.75)

I am requesting funds to hire an undergraduate student for 7 hours per week to help with recruitment and the intervention for 19 weeks at \$10/hr. ($\$10 * 19 * 8 = \$1330 + 7.65\% = \$1,431.75$).

Graduate student (nurse practitioner) (\$280)

I would like to hire nurse practitioner students for the blood draws. I estimate that each blood draw will take 15 minutes, which adds up to 10 hours for 39 participants before and 10 hours after the intervention for a total of 20 hours. ($\$13/h for 20 hours = \$260 + 7.65\% = \$280$)

Laboratory supplies

Assay kits for assessment of blood markers (\$2,362)

CRP: 1 kit for 36 samples at \$479, need 2 kits = \$958, Insulin: 1 kit for 36 samples at \$449, need 2 kits = \$898, LPS: 1 kit for 36 samples at \$253, need 2 kits - \$506

Blood and stool collection supplies (\$433)

Needles, tubes, tourniquets: \$150, Tubes to store serum in ultracold freezer: \$159, Stool collections cups and hats: \$108, Tongue depressors: \$16

Microflora analysis (\$8,500)

DNA extraction of stool samples: \$900

Sequencing for identification of microflora \$1,500 per 17 samples, we will have a total of 84 samples: \$7,500

Shipping (overnight) of stool samples to Minnesota: \$100

Vegetables (\$900)

Commercial sauerkraut for non-fermented vegetables group (\$44.30 per 384 oz – need 223 oz per person for the entire study, $223 \times 13 \text{ people} = 2899 \text{ oz} = 8 \text{ cases}$): \$355

Fermented vegetables (\$29 per 256 oz – need 223 oz per person for the entire study): \$377

Storage containers: (need 1 cup containers: 42 days \times 39 participants = 1638 containers, \$24 per case of 240, need 7 cases): \$168

Participant compensation (\$780)

\$20 dollars for completing the study, \$5 for completing baseline measures and \$15 for completing the 6 weeks. Compensation will be pro-rated if participants drop out before 6 weeks.

Car mileage (\$288.90)

Vegetables samples will be delivered to participants weekly for 6 weeks. Assuming that we will drive 15 miles for every 5 participants per week = 15 miles \times 6 (28 participants in the vegetables groups divided by 5 = 6) \times 6 weeks = 540 miles \times \$0.535 = \$288.90

Bibliography

2. Ogden, C. L., Carroll, M. D., Fryar, C. D., and Flegal, K. M. (2015) Prevalence of obesity among adults and youth: United states, 2011-2014. *NCHS Data Brief* **(219)**, 1-8.
3. Bradlow, H. L. (2014) Obesity and the gut microbiome: Pathophysiological aspects. *Hormone Molecular Biology and Clinical Investigation* **17**, 53-61.
5. Turnbaugh, P. J., Ley, R. E., Mahowald, M. A., Magrini, V., Mardis, E. R., and Gordon, J. I. (2006) An obesity-associated gut microbiome with increased capacity for energy harvest. *Nature* **444**, 1027-1031.

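### A rise in Bifidobacteria and Lactobacilli in stool taken at the end of feeding may partly or wholly be food bacteria in transit, and the plan has no step to tell the two apart

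*Combined protocol and SAP*

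**What the plan says.** Under Study Aims, Aim 2 concerns the effect of six weeks of daily consumption on the gut microflora profile, and Hypothesis 2 predicts its direction: "Consumption of fermented vegetables will lead to a shift in microbial communities towards an increase in communities regarded as probiotics such as Bifidobacteria and Lactobacilli".

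Five other statements bear on how that prediction is tested.

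- **Test food** (Vegetables preparation): "The process of vegetable fermentation involves *Lactobacilli* and *Bifidobacteria* that are naturally found on the leaves of cabbage, carrots and on cucumbers".
- **Comparator food** (same section): "it will have a similar flavor but no live microorganisms", because it is made with acetic acid.
- **Exposure** (Study design): women in the vegetable groups are "asked to consume 1 cup of vegetables (140 g) per day for the entire duration of the study".
- **Sampling** (Study design): "Biological samples including feces and blood samples will be collected at baseline, before randomization and at the end of the 6-week intervention". No stool after feeding has ended is described, and no interval between the last portion and the final stool is given.
- **Assay** (Microflora analysis and Project budget): "DNA will be extracted using the QIAamp DNA stool mini kit", followed by "Sequencing for identification of microflora". No culture or viability step is described, and the taxonomic depth is not stated.

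The Microflora analysis section also says: "Analysis of microflora in stool samples and vegetables samples will be conducted". The Analysis section lists analysis of variance at both time points, paired t tests, and Pearson correlations that involve changes in the microflora. It gives the vegetable data no role.

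**The concern.** The intervention delivers the bacteria that serve as its own outcome. Stool collected while the food is still being eaten, or very soon after, can contain bacteria that have only passed through. Sequencing of extracted DNA counts these together with residents, whether they are alive or dead.

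Randomisation does not remove this, because the signal arises from the allocated food and not from who was allocated. Regular eaters of fermented vegetables are excluded at entry, so baseline stool should carry little from this source. A transit signal would therefore also appear as a change from baseline.

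What is at stake is the wording of the Aim 2 result. Followed as written, the plan could report a shift in the gut community when the resident community had not changed. The planned correlations between clinical or laboratory measures and microflora changes would take in the same signal. The distinction also matters to the plan's own rationale, since the Significance section faults weight-loss trials for effects that do not outlast the intervention.

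**Working it through.** **1. The chain, side by side.**

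| Link | What the documents give | What they leave open |
|---|---|---|
| Outcome | Bifidobacteria and Lactobacilli | Taxonomic level |
| Test food | Fermentation involving those two groups | Bacterial load |
| Comparator | No live microorganisms | Bacterial DNA content |
| Stool timing | Baseline and end of six weeks | Gap after last portion |
| Assay | DNA extraction and sequencing | Depth; whether variants can be matched |
| Vegetable microflora | Will be analysed | Number of samples; how results are used |

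No entry in the middle column separates transit from residence. The one item that could do so, the vegetable microflora, has no stated use.

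**2. Possible size of the food contribution.** The documents give only the 140 g daily portion. The other inputs are assumptions: 10^6 to 10^8 bacteria per gram of vegetable, 5×10^12 to 1.5×10^13 bacterial cells in a day's stool, and full survival of the DNA.

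Added share = 140 × (bacteria per g) ÷ (cells per day's stool)

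- Low: 140 × 10^6 ÷ 1.5×10^13 = 1.4×10^8 ÷ 1.5×10^13 = 0.0009%
- High: 140 × 10^8 ÷ 5×10^12 = 1.4×10^10 ÷ 5×10^12 = 0.28%

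Against an assumed resident Lactobacillus share of 0.01% to 0.5%, the ratio runs from 0.0009 ÷ 0.5 = 0.002 (negligible) to 0.28 ÷ 0.01 = 28. No comparable figure is offered for Bifidobacteria. A range this wide shows that the question is open, not that the effect is large.

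**3. What a given transit signal would do to the test.** The plan states no alpha, SD or power, so there is no figure of its own to reproduce. Assumptions: two-sided alpha 0.05, 13 women per arm, no change in residents, and a transit signal of d between-woman SDs in the fermented arm relative to both other arms.

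- Two-arm t test: noncentrality = d × √(13/2), 24 df
- Three-arm analysis of variance: noncentrality = 13 × (2/3) × d², 2 and 36 df

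| d | t test significant | ANOVA significant |
|---|---|---|
| 0 | 5% | 5% |
| 0.25 | 9.4% | 8.9% |
| 0.5 | 23.2% | 22.5% |
| 0.8 | 49.9% | 51.2% |
| 1.0 | 68.7% | 71.6% |
| 1.5 | 95.6% | 97.4% |

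The value of d is not known. If the comparator also contributes bacterial DNA, d for the fermented versus non-fermented contrast is smaller.

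**4. The sequencing count.** The budget prices sequencing at $1,500 per 17 samples and gives $7,500 for 84. This reproduces: 84 ÷ 17 = 4.94, rounded up to 5 batches, and 5 × 1,500 = 7,500. The origin of 84 is unclear:

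- 39 women × 2 stools = 78, leaving 84 − 78 = 6 that could be vegetable samples; or
- the Car mileage line counts 28 women in the vegetable groups, that is 14 per arm and 3 × 14 = 42 in all, and 42 × 2 = 84 leaves none.

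The cost does not settle it, because 78 samples also need 5 batches and cost $7,500.

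**The case against.** The strongest reply is that the plan does not claim what is being questioned. Aim 2 asks what daily consumption does to the microflora profile. Neither it nor Hypothesis 2 mentions residents, colonisation or persistence. On that reading, bacteria found in stool during feeding are part of the effect, and stool at the end of feeding measures it correctly. This stands in part: it is why the all-taxa comparison should remain primary and why the point concerns interpretation. It does not dispose of the matter, because a result reported as a shift in microbial communities will be taken to mean more than food in transit.

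Three stronger readings are tempting, and the documents do not support them.

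- A reader might infer that the artefact affects the fermented arm only. The comparator is said to lack live organisms, which does not mean that it lacks bacterial DNA, and sequencing does not require live cells. The budget describes it as commercial sauerkraut. A lower load is plausible, but no figure is given for either food.
- A reader might infer from the tables above that a false positive is likely. Every biological input and every value of d is assumed.
- A reader might infer that a shift should be concluded only if it survives removal of everything found in the vegetables. If removal were done by genus, it could delete the whole endpoint, because the plan names both target groups as fermenters. Even at variant level it would discard residents that share a sequence with the food.

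It can also be said that a safeguard exists, since vegetable samples are to be analysed, and that this is a small study expected to yield pilot data. Both are true. But data with no pre-specified use do not protect the conclusion, and specifying the use costs little.

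**Conclusion.** The point holds as a limit on what the Aim 2 result can mean. The overlap between outcome and food, the sampling at the end of feeding, the DNA readout and the absence of any role for the vegetable data all come from the documents. Together they mean that an observed rise could partly or wholly be transit.

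The size is unknown. The documents give no bacterial load, resident share or SD, and under the assumed inputs the food contribution runs from negligible to many times the resident Lactobacillus share. The arm difference is probably in the hypothesised direction, but this rests on the comparator carrying less bacterial DNA, which is not stated.

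The documents do not show that Hypothesis 2 is untestable, that a spurious finding is to be expected, or that six sequencing places are free for vegetables. The point is a cheap improvement to the analysis plan and does not call for a redesign.

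**What to change.** 1. Keep the comparison of all Bifidobacteria and Lactobacilli as the primary analysis of Hypothesis 2.
2. Pre-specify a sensitivity analysis, using the vegetable microflora data already planned, that excludes stool sequence variants matching those in the fermented vegetables. Match at variant level, not by whole genera. Report also whether the matching variants were already present at baseline.
3. Pre-specify the wording. If the increase is confined to food-matching variants, or if the sequencing depth does not allow variant matching, limit the conclusion to bacteria detected in stool while the food is being eaten. Apply the same caveat to the Pearson correlations.
4. Record the dates of the last portion and of the final stool.
5. Reconcile the 84 budgeted samples (78 stools plus 6, or 42 × 2) and state how many vegetable samples will be sequenced. The food is supplied weekly, so a handful of samples may not represent all the batches eaten.

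The cost is a small amount of extra analysis and two recorded dates, with no added visit or participant and no change to feeding. If the 84 turn out to be all stools, the vegetable sequencing that the protocol already promises is not covered by that budget line. The sensitivity analysis is conservative: it also removes food strains that truly colonised and residents that share a sequence with the food. For that reason it accompanies the primary analysis and does not replace it.

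### The week-6 ANOVA has no BMI or baseline term, so a chance BMI imbalance between vegetable arms of 13 passes straight into the result

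*Combined protocol and SAP*

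**What the plan says.** - **Allocation.** Study design: "39 women will be randomized into one of three treatment groups", 13 in each. The eligibility table admits BMI 26 to 40 kg/m2. No stratification, blocking, sequence method or concealment is described.
- **Timing.** Study procedures: "once all eligibility criteria are confirmed, participants will be randomized into one of the three groups". BMI is one of those criteria, so it is known before allocation. Study design also places baseline blood and stool collection before randomisation.
- **Contrast of interest.** Aim 1 concerns "daily consumption of fermented vegetables compared with non-fermented vegetables for 6 weeks on markers of metabolic syndrome and inflammation". Aim 2 makes the same comparison for the gut microflora. Both are 13 versus 13.
- **Analysis.** Arms are compared by analysis of variance at each of the two time points, and changes within each arm by paired t tests. No covariate is named.
- **Link to obesity.** The background says that "overweight and obese individuals often present elevated levels of inflammatory markers in the blood, including LPS" and also names CRP. The Significance section refers to a "strong relationship between the gut bacteria and obesity". The remaining outcomes come only under "other biological and clinical parameters associated with obesity and other chronic diseases".

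**The concern.** The trial's premise is that weight status goes with the microflora and inflammatory markers it will measure. With 13 women per arm, chance alone can leave one vegetable arm noticeably heavier than the other.

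Nothing in the analysis would take that difference out. The week-6 ANOVA compares raw means. The baseline ANOVA may reveal an imbalance but does not correct for it. The paired t tests look within each arm, so they do not estimate fermented against non-fermented vegetables. A reader of the final report could not separate a modest effect of fermentation from a difference in BMI present at entry.

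**Working it through.** **Inputs from the documents.** 39 women, three arms of 13 (3 × 13 = 39), BMI range 26 to 40. The plan gives no BMI mean or SD, share obese, BMI-outcome correlation, alpha, power or effect size, so its sample size cannot be reproduced beyond that sum.

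**Assumptions, shown as ranges.** BMI SD 3.0 to 4.04 kg/m2 (4.04 is a uniform spread over 26 to 40: 14/√12); BMI-outcome correlation ρ of 0.3 to 0.8; 31 to 69% of the women obese; two-sided alpha 0.05.

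**Step 1. Chance difference in mean BMI between the vegetable arms.** SE = SD × √(2/13) = SD × 0.392, by normal approximation.

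| BMI SD | SE | 95% range of chance difference | P(difference > 2 kg/m2) |
|---|---|---|---|
| 3.0 | 1.18 | ±2.3 | 9% |
| 3.5 | 1.37 | ±2.7 | 15% |
| 4.04 | 1.58 | ±3.1 | 21% |

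Counting obese women instead (exact multivariate hypergeometric, 12 to 27 obese of 39), the two arms differ by 3 or more in about 30 to 33% of allocations and by 4 or more in 14 to 17%.

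**Step 2. How much reaches the outcome.** With no adjustment, the expected shift in outcome SDs is ρ × (BMI difference / BMI SD). For a 2 kg/m2 difference:

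- SD 4.04: 0.3 × 2/4.04 = 0.15; 0.5 × 2/4.04 = 0.25
- SD 3.0: 0.3 × 2/3.0 = 0.20; 0.5 × 2/3.0 = 0.33

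The unadjusted SE of the arm contrast is itself √(2/13) = 0.39 outcome SD. The shift is thus smaller than one standard error, but it is not negligible.

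**Step 3. Type I error (20,000 simulated trials, uniform BMI).** Averaged over all randomisations it is about 5%. Among trials where the arms happen to differ by more than 2 kg/m2 it is about 7% at ρ = 0.3 and about 10% at ρ = 0.5.

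**Step 4. What adjustment recovers (20,000 simulated trials).** SE of the fermented versus non-fermented contrast, in outcome SDs:

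| ρ | Unadjusted | Continuous BMI in model | BMI split at 30 in model |
|---|---|---|---|
| 0.3 | 0.39 | 0.38 | 0.39 |
| 0.5 | 0.39 | 0.35 | 0.37 |
| 0.8 | 0.39 | 0.24 | 0.31 |

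**Step 5. What stratification adds.** Permuted blocks of 3 within two strata cut at BMI 30 reduce the SD of the between-arm BMI difference from about 1.58 to 1.03 kg/m2. The chance of a difference above 2 kg/m2 falls from about 20-21% to 5%. It does not reach zero, because BMI still varies within each stratum.

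**The case against.** Four objections deserve weight.

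- **The plan's rationale is mostly about lean versus non-lean.** The Bifidobacteria statement sets overweight and obese people together against lean people, and the LPS and CRP statement groups overweight with obese. Every participant has a BMI of at least 26. The documents therefore state no gradient across BMI 30, and a list such as "The composition of the intestinal bacteria is influenced by several factors, including host genotype, age, sex, antibiotic/medication use, disease, and diet" does not include BMI. This stands. It weakens the case for a stratum cut at 30 and is one reason to show results over a range of correlations. It does not make an unadjusted comparison preferable.
- **Randomisation already protects the test.** True on average, as Step 3 shows. A reader might infer that the plan inflates the false-positive rate; it does not.
- **Stratifying 39 women in a study meant to yield pilot data is optional.** Accepted. Small blocks also make the next assignment easier to guess for anyone who knows the past ones: about 56-57% correct with blocks of 3 and 6 in two strata, against 44% for an unblocked 13/13/13 list.
- **The baseline value of each outcome would do the job without BMI.** Largely so, and it belongs in the same model.

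A reader might also infer that allocation is unconcealed or the trial open. The documents do not say so: they are silent on concealment and on blinding. Women in the usual-diet arm plainly know that they receive no vegetables, but that does not settle who can foresee an assignment. Nor can it be said that every main outcome is tied to obesity. No outcome is designated as main or primary, and for blood pressure and insulin the link is generic.

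**Conclusion.** The point holds as one about analysis. A BMI difference above 2 kg/m2 between the vegetable arms has a probability of about 9 to 21%, depending on an assumed SD of 3.0 to 4.04, and the planned ANOVA would pass it on. The result would be a shift of roughly 0.15 to 0.33 outcome SD at an assumed correlation of 0.3 to 0.5. Average type I error is unaffected; what suffers is precision and the interpretation of this single trial.

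The gain from adjustment depends on how strongly BMI relates to each outcome: close to nothing at a correlation of 0.3, a fall in SE from 0.39 to about 0.35 SD at 0.5, and to 0.24 at 0.8. The documents give no such correlation and no change in CRP or LPS per BMI unit, so the effect cannot be put in the units of any marker. The missing description of sequence generation and concealment is a gap in reporting, not evidence of a flaw in conduct.

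**What to change.** **Main change.** Replace the week-6 ANOVA with a linear model of the week-6 value on arm and continuous baseline BMI, preferably with the outcome's own baseline value as well, and report the fermented versus non-fermented contrast from it. Keep BMI continuous: the split at 30 loses part of the gain (Step 4). BMI is needed to confirm eligibility, blood and stool are taken before randomisation, and the planned baseline comparison already requires baseline clinical measures, so no new data are needed. The cost is one or two degrees of freedom: residual degrees of freedom go from 39 − 3 = 36 to 35 or 34 if all women complete.

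**Optional.** Stratify on one BMI cut (below 30, 30 or above) in permuted blocks of undisclosed size, and keep BMI in the model. With blocks of 3 and 6, arm totals usually fall at 12 to 14 but can reach 11 to 15 (outside 12 to 14 in about 2 to 5% of simulated runs). A 14th woman in the non-fermented arm would need 14 × 223 = 3,122 oz, against 8 × 384 = 3,072 oz in the Project budget, so one extra case should be allowed for.

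**Reporting.** State how the sequence is generated, who holds it, and when the next assignment is released. This costs a few sentences.
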